4.4 Toxicity Management & Dose Delays/Modifications/Discontinuation

Any subject who receives at least one dose of study therapy will be evaluable for toxicity endpoints. Each subject will be assessed for the development of toxicity according to the timeframe referenced in [Section 5.0](#) Study Procedures Table). Toxicity will be assessed according to CTCAE v.5.0.

The following should be taken into consideration in decisions regarding dose modifications (reductions or interruption) (please refer to [Appendix A](#) for dose modification algorithms for potential combination treatment related adverse events).

As a general approach all AEs should be managed with supportive care at the earliest signs of toxicity considered related to the study treatment. Should this be ineffective, dose interruptions and/or reductions should be considered to prevent worsening of toxicity.

The assigned starting dose for cabozantinib is 40mg/day. 20 mg dose reduction level of cabozantinib is permitted (see Table 0-1).

Dose modification criteria for cabozantinib are shown in Table 0-2. Dose interruptions and/or reductions should be implemented for unacceptable toxicity. Doses may be modified at any time while a subject is on treatment.

Dose reductions or interruptions may also occur in the setting of lower grade toxicity than defined in Table 0-2, if the investigator feels it is in the interest of a subject's safety and will optimize drug tolerability.

Interruption of cabozantinib treatment for cabozantinib-related AEs may occur at any time per investigator discretion. If treatment is interrupted due to related AEs for more than 6 weeks, cabozantinib should be discontinued unless there is unequivocal evidence that the subject is benefitting. In this situation, a subject may be able to restart therapy with a dose reduction upon resolution of the toxicity per the discretion of the investigator.

Dose interruptions for reason(s) other than related AEs (e.g., surgical procedures) can be longer than 6 weeks per the discretion of the investigator.

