
^a Study treatment dose adjustment is only needed if the toxicity was deemed related to cabozantinib treatment or had an unclear relationship to cabozantinib treatment.
 
See Section 4.4.3 for additional instructions for management of cabozantinib related adverse events
	

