4.4.1 Cabozantinib Dose Reinstitution and Reescalation

See [Section 4.4](#) for permitted timeframes for dosing delays and interruptions.

If the subject recovers from his or her toxicities to CTCAE v.5.0 Grade ≤ 1 or to the baseline value (or lower) and the toxicity was unrelated to study treatment, then study treatment may be restarted with no change in dose.

If the subject recovers from his or her toxicities to Grade ≤ 1 or to the baseline value (or lower) the toxicity was deemed possibly related to study

treatment, then study treatment may be restarted at a reduced dose (see Table 0-1 for the schedule of dose reductions).

Subjects receiving a daily dose of 20 mg may be restarted at the same dose if deemed safe at the discretion of the investigator. Subjects unable to tolerate a daily dose of 20 mg should discontinue study treatment.

Re-escalation to the previous dose, (but not higher than 40 mg/day) may be allowed at the discretion of the investigator for AEs which have resolved or recovered to Grade 1 (or baseline value) and deemed tolerable and easily managed by optimized supportive treatment. Dose re-escalation is not allowed for a drug-related dose reduction triggered by Grade 4 hematologic toxicities or by Grade 4 AEs affecting major organs (e.g., central nervous system, cardiac, hepatic, and renal).

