4.4.3.13 Hepatocellular Toxicity

Investigators should monitor for DILI diligently and report any potential events. Elevation of aminotransferases (ALT and AST) and bilirubin have been observed during treatment with cabozantinib. It is recommended that subjects with elevations of ALT, AST, and/or bilirubin have more frequent laboratory monitoring of these parameters. If possible, hepatotoxic concomitant medications should be discontinued in subjects who develop increased values of ALT, AST, or bilirubin, and other potential causes for these increases (e.g., cancer-related, infection) should be evaluated. See Table 0-7 for management of hepatocellular toxicity.

Table 0-7 Management of Hepatocellular Toxicity Associated with Cabozantinib

Event – Elevation of ALT, AST, or Total Bilirubin (CTCAE v4)	Management

Grade 1
 
ALT or AST > ULN – 3.0 x ULN
 
Bilirubin > ULN – 1.5 x ULN
	
 • Dose adjustment is usually not required. • Consider discontinuing concomitant hepatotoxic medications and add supportive care as indicated.

Grade 2^{a,b}
 
ALT or AST > 3.0 – 5.0 x ULN
 
Bilirubin > 1.5 – 3.0 x ULN
	
 • Interrupt cabozantinib if lasting longer than 1 week and consider more frequent monitoring of ALT, AST, and bilirubin. • Restart cabozantinib after lab abnormalities have resolved to at least CTCAE Grade ≤ 1 or baseline.

Grade 3^{a,b}
 
ALT or AST > 5.0 – 20.0 x ULN
 
Bilirubin > 3.0 – 10.0 x ULN
	
 • Interrupt cabozantinib and consider more frequent monitoring of ALT, AST, and bilirubin. • Restart cabozantinib at a reduced dose after lab abnormalities have resolved to at least CTCAE Grade ≤ 1 or baseline. • Discontinue if lab abnormalities cannot be reversed despite interruption of study treatment.

Grade 4^b
 
ALT or AST > 20.0 x ULN
 
Bilirubin > 10 x ULN
	
Subjects should have cabozantinib interrupted immediately. Discontinue cabozantinib unless the following criteria are met:
 
 • Subject is deriving clear clinical benefit as determined by the Investigator, and approved by the Principal Investigator. • Toxicity can be managed with a dose reduction following recovery to Grade 1 (or baseline) and optimal medical care.

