Grade 2	
 • Cabozantinib treatment may be continued if PPES is tolerated. • Cabozantinib should be dose reduced or interrupted if PPES is intolerable. • Continue urea 20% cream twice daily AND high potency steroid cream (e.g., clobetasol 0.05%) once daily and add analgesics (e.g., NSAIDs/gamma-aminobutyric acid agonists) for pain control if needed. 
Reassess at least weekly; if PPES worsens or affects self-care, proceed to the intervention guidelines for Grade 3.
 
 • Continue temozolomide at the investigator's discretion
Grade 3	
 • Interrupt cabozantinib treatment until severity decreases to Grade 1 or 0. • Continue treatment of skin reaction with high potency steroid cream (e.g., clobetasol 0.05%) twice daily AND analgesics. • Resume study drug at a reduced dose if PPES recovers to Grade ≤ 1. • Discontinue subject from study treatment if PPES does not improve within 6 weeks • Interrupt/continue temozolomide at the investigator's discretion
Proteinuria (UPCR)	
≤ 1 mg/mg (≤ 113.1 mg/mmol)	
 • No change in cabozantinib or temozolomide treatment
> 1 and < 3.5 mg/mg (> 113.1 and < 395.9 mg/mmol)	
 • Refer to Table 0-6 for the management of cabozantinib treatment. No change in temozolomide treatment
≥ 3.5 mg/mg (≥ 395.9 mg/mmol)	
 • Refer to Table 0-6 for the management of cabozantinib treatment. No change in temozolomide treatment.
Nephrotic syndrome	
 • Discontinue cabozantinib
Hepatocellular Toxicity	
Grade 2 AST or ALT or Total Bili lasting longer than a week	
 • Interrupt cabozantinib and temozolomide until Grade 1. • Refer to the Section 4.4.3.13 for the management of DILI
Other Treatment Related Adverse Events (such as fatigue, nausea, vomiting, anorexia, weight loss, etc)	

Grade 1 or Grade 2 (tolerable)	
 • Add supportive care as indicated. • Continue cabozantinib and temozolomide treatment at the current dose; monitor as clinically indicated

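### For prolonged Grade 2 liver tests, Appendix A and Table 0-7 give different cabozantinib rules with no stated precedence, and Table 0-8 assigns Grade 3 to both stopping and reducing temozolomide

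*Combined protocol and SAP*

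**What the plan says.** **Grade 2 liver tests lasting over a week.** Two places cover this event.

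- Appendix A, Hepatocellular Toxicity row: "Interrupt cabozantinib and temozolomide until Grade 1". The row's only cross-reference is "Refer to the Section 4.4.3.13 for the management of DILI".
- Section 4.4.3.13, Table 0-7, Grade 2 row: cabozantinib is interrupted if the abnormality lasts longer than a week, then "Restart cabozantinib after lab abnormalities have resolved to at least CTCAE Grade ≤ 1 or baseline". Note a, attached to this row, says that when hepatic metastases are present an aminotransferase rise of less than a doubling from baseline may need no dose change, provided bilirubin and coagulation factors are not progressively rising.

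Section 4.4.1, the general restart section, also accepts recovery to Grade 1 or below "or to the baseline value (or lower) the toxicity was deemed possibly related to study" treatment.

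**Routing.** Section 4.4 points to Appendix A "for dose modification algorithms for potential combination treatment related adverse events". The note under Table 0-2 points to Section 4.4.3 "for additional instructions for management of cabozantinib related adverse events".

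**Temozolomide.** In the non-hematological row of Table 0-8 (Section 4.4.4), Grade 2 means interruption, Grade 3 or 4 means discontinuation, and Grade 3 also means a one-level reduction. Treatment continues only at Grade 1 or below.

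**Grading version.** Section 4.4 states "Toxicity will be assessed according to CTCAE v.5.0". The event column of Table 0-7 is headed "Elevation of ALT, AST, or Total Bilirubin (CTCAE v4" and prints its own limits.

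**The concern.** This is a multicenter trial, so two sites that start from different pages can handle the same liver value differently. Appendix A read on its own does not let a subject back onto cabozantinib at a baseline that already lies above Grade 1. Inclusion criterion 6 admits such subjects, because bilirubin may be up to 3 x ULN in Gilbert's disease. Appendix A also has no counterpart to the liver-metastasis note.

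The direct risk is an unneeded hold. A longer consequence is possible: Section 4.4 discontinues cabozantinib after more than 6 weeks of interruption for related events unless benefit is unequivocal.

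For temozolomide, a site that reads Table 0-8 for a Grade 3 liver event finds two incompatible instructions, and the Appendix A liver row gives no Grade 3 instruction to settle them.

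**Working it through.** The plan states no figure to reproduce on this point. The check is a comparison of texts, followed by bounds on who can be affected.

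**1. Same trigger, different cabozantinib rule**

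| | Appendix A liver row | Table 0-7, Grade 2 |
|---|---|---|
| Trigger | Grade 2 AST, ALT or bilirubin for over a week | Same |
| Restart | Grade 1 | Grade 1 or below, or baseline |
| Liver-metastasis note | None | Note a: change may not be needed |

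Section 4.4.1 agrees with Table 0-7 on baseline.

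**2. Is there a rule of precedence?** None was found. The two pointers in Section 4.4 lead to different places and neither ranks them. The liver row's reference to Section 4.4.3.13 is limited to DILI, which is the separate discontinuation condition in Table 0-7 note b. By contrast, the Appendix A proteinuria rows hand cabozantinib management over to Table 0-6. The missing baseline alternative is not a convention of Appendix A either, because its Grade 4 cabozantinib row allows recovery to Grade 1 or baseline.

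**3. Who can be affected?** This step assumes that the limits printed in Table 0-7 also define Grade 2 in Appendix A, which prints none. In multiples of ULN, bilirubin Grade 1 runs to 1.5 and Grade 2 to 3.0; ALT/AST Grade 1 runs to 3.0 and Grade 2 to 5.0.

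- *Restart.* Entry ALT/AST is capped at 3.0, and entry bilirubin at 1.5 outside Gilbert's disease. Both caps lie within Grade 1 or below, so baseline adds nothing for those subjects. In Gilbert's disease the cap is 3.0. With baseline b, the restart rules differ only if b > 1.5, and a rise that stays Grade 2 needs b < 3.0. Hence 1.5 < b < 3.0. Example: b = 2.0, a rise to 2.8 for over a week, then a return to 2.0. Table 0-7 restarts cabozantinib; Appendix A read literally waits for 1.5.
- *Liver metastases.* A Grade 2 value that is less than a doubling needs 3.0 < value < 2b, so b > 1.5, and entry allows b up to 3.0. Example: 2.5 rising to 4.5, a ratio of 4.5/2.5 = 1.8. Note a may permit no change; Appendix A holds both drugs.

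If the version 5.0 limits apply to Appendix A instead, the documents do not print them and these bounds cannot be confirmed.

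**4. Table 0-8.** The two hematological rows keep discontinuation and reduction apart: ANC below 0.5 versus 0.5 to below 1.0, and platelets below 10 versus 10 to below 50 (x 10⁹/L). Only the non-hematological row overlaps, at Grade 3. In Appendix A, the diarrhea row reduces temozolomide one level at Grade 3 and discontinues it at Grade 4, and the row for other treatment-related events does the same for temozolomide-related toxicity. The liver row covers Grade 2 only.

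**The case against.** The case for leaving the text alone has several sound parts.

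- **The body text already favours baseline.** Section 4.4.1 and Table 0-7 agree, and the liver row leads the reader to the section that contains Table 0-7. This makes the probable intent clear and the defect a drafting omission. It does not remove the conflict, since the reference is for DILI only.
- **Note a is permissive.** A reader might infer that one place forbids what the other demands. That is too strong: a site that holds cabozantinib complies with both. Only a site that continues under note a departs from Appendix A. Section 4.4 also presents this material as something to consider in dose decisions and gives the investigator discretion to interrupt.
- **Relatedness limits the row.** The closing note of Appendix A confines adjustment to toxicity related to cabozantinib or of unclear relationship, so a rise attributed to metastases falls outside it.
- **A stricter combination rule could be deliberate.** Section 8.2.2 warns of fatal and severe hepatotoxicity with temozolomide. The documents do not give this as the reason, but it bears on the remedy. A reader might infer that temozolomide should also restart at baseline in Gilbert's subjects. Nothing in the documents supports loosening that safety rule.
- **Appendix A already answers Grade 3 elsewhere.** This is true for diarrhea and other events, and it shows which way to resolve Table 0-8. It does not reach the liver row.

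**Conclusion.** The point holds as a minor inconsistency in dosing instructions. For one liver event, the plan gives two cabozantinib restart rules and an unmatched liver-metastasis note, and ranks neither place over the other. Table 0-8 separately contradicts itself at Grade 3.

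Reach is narrow: some Gilbert's subjects, and some liver-metastasis subjects with raised baseline enzymes. The documents do not say how many there will be. Even these groups are identified only on the assumption that Table 0-7's printed limits apply to Appendix A, so no percentage or expected count is offered.

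Two stronger readings are not supported. A reader might infer that Appendix A forces affected subjects off cabozantinib for good. Section 4.4 excepts unequivocal benefit, and the 6-week rule in Section 4.8 applies only where toxicity has not recovered to tolerable Grade 2 or below, so a stop is possible but not certain. A reader might also infer bias in the 12-week progression-free result. Nothing in the documents shows such an effect, and none is claimed.

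**What to change.** 1. In the Appendix A liver row, for cabozantinib only, write: *until Grade ≤1 or baseline; see Table 0-7 and its notes*. This follows the way the proteinuria rows refer to Table 0-6. Leave the temozolomide rule of Grade 1 or below unchanged.
2. In the non-hematological row of Table 0-8, make Grade 3 a hold with a one-level reduction and keep discontinuation for Grade 4, to match Appendix A. The sponsor should confirm that this also holds for liver toxicity.
3. Reconcile the version 4 heading and printed limits of Table 0-7 with the version 5.0 grading used elsewhere, so that one set of limits applies to all three places.

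The cost is amendment wording in the liver row, Table 0-7 and Table 0-8, plus the sponsor's confirmation under item 2 and a decision on the limits under item 3. No visits, tests or subjects are added.

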4.4.4 Management of Temozolomide Related Adverse Events

The most common adverse reactions ($\geq 10\%$ incidence) are: alopecia, fatigue, nausea, vomiting, headache, constipation, anorexia, convulsions, rash, hemiparesis, diarrhea, asthenia, fever, dizziness, coordination abnormal, viral infection, amnesia, and insomnia.

The most common Grade 3 to 4 hematologic laboratory abnormalities ($\geq 10\%$ incidence) that have developed during treatment with temozolomide are: lymphopenia, thrombocytopenia, neutropenia, and leukopenia.

Allergic reactions have also been reported.

Please refer to [Appendix A](#) for dose modification algorithms for potential combination treatment related adverse events.

Table 0-8: Temozolomide Dosing Interruption or Discontinuation during Treatment Period

Toxicity	Temozolomide Interruption	Temozolomide Discontinuation	Reduce Temozolomide by 1 Dose Level
Absolute Neutrophil Count (ANC)	≥ 0.5 and $< 1.5 \times 10^9/L$	$< 0.5 \times 10^9/L$	≥ 0.5 and $< 1.0 \times 10^9/L$
Platelet Count	≥ 10 and $< 100 \times 10^9/L$	$< 10 \times 10^9/L$	≥ 10 and $< 50 \times 10^9/L$
NCI-CTCAE non-hematological toxicity (except for alopecia, nausea and vomiting)	Grade 2	Grade 3 or 4	Grade 3

Treatment with temozolomide may be continued when all of the following conditions are met:

- $ANC \geq 1.5 \times 10^9/L$
- Platelet count $\geq 100 \times 10^9/L$
- NCI-CTCAE non-hematological toxicity \leq Grade 1 (except for alopecia, nausea and vomiting)

Table 0-9: Temozolomide Dose Levels

Dose 0 (Assigned Starting Dose)	Dose Level 1	Dose Level 0	Dose Level -1
150 mg/m ² /day	200 mg/m ² /day	150 mg/m ² /day	100 mg/m ² /day

Please see [Appendix B](#) for Daily Dose Calculations by Body Surface Area (BSA).

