40. Schiff, D., et al., Phase 1 dose escalation trial of the safety and pharmacokinetics of cabozantinib concurrent with temozolomide and radiotherapy or temozolomide after radiotherapy in newly diagnosed patients with high-grade gliomas. *Cancer*, 2016. 122(4): p. 582-7.
doi:10.1097/CAD.000000000000108

APPENDIX A - DOSE MODIFICATION ALGORITHMS FOR POTENTIAL COMBINATION TREATMENT RELATED ADVERSE EVENTS

AE Terms & Descriptions	Dose Modification Algorithms
Diarrhea	
a. Grade 1-2 (duration < 48 hr)	a. Continue Cabozantinib at the current dose. If it does not improve with supportive measures consider a dose reduction. Continue temozolomide at the current dose.
b. Intolerable Grade 2 or Grade 3	b. Interrupt Cabozantinib and temozolomide until Grade ≤ 1 then consider restarting Cabozantinib at reduced dose. Dose reduce temozolomide by one dose level for Grade 3 only. Discontinue temozolomide for grade 4.
	c. Refer to the Table 0-3 for the management of diarrhea.
Neutropenia	
a. Neutrophil count <1.5	a. Interrupt temozolomide and cabozantinib until neutrophil count $\geq 1.5 \times 10^9/L$.
b. Neutrophil count <1.0	b. Interrupt temozolomide and cabozantinib until $\geq 1.5 \times 10^9/L$. Reduce temozolomide by 1 dose level. Continue cabozantinib at the same.
c. Neutrophil count <0.5	c. Discontinue temozolomide, interrupt cabozantinib until neutrophil count is $\geq 1.5 \times 10^9/L$ then resume at same dose.
Febrile Neutropenia	
Grade 3 or 4	Interrupt temozolomide and cabozantinib until resolved. Upon resumption, reduce temozolomide by 1 dose level. Continue cabozantinib at the same dose.
Thrombocytopenia	
Grade 1 or 2	Interrupt temozolomide until $\geq 100 \times 10^9/L$. Continue cabozantinib.

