Grade 3 or 4	Interrupt temozolomide and cabozantinib until $\geq 100 \times 10^9/L$. Dose reduce temozolomide by 1 dose level. Continue cabozantinib at the same dose or reduce dose by one level-at the investigator's discretion. At platelet count of $< 10 \times 10^9/L$ discontinue temozolomide.

Hypertension	
> 140 mm Hg (systolic) ^a and < 160 mm Hg OR > 90 mm Hg (diastolic) and < 110 mm Hg	
 Optimize antihypertensive therapy. Reduce cabozantinib treatment by one dose level if optimal antihypertensive therapy (usually to include 3 agents) does not result in BP <140 mm Hg systolic or <90 mm Hg diastolic. Continue temozolomide at the current dose
≥ 160 mm Hg (systolic) OR ≥ 110 mm Hg (diastolic)	
 Reduce cabozantinib by one dose level or interrupt cabozantinib treatment per investigator discretion. Re-start cabozantinib treatment at the most tolerable dose and re-escalate only if BP falls to and is sustained at < 140 mm Hg systolic and < 90 mm Hg diastolic. 
Interrupt/continue temozolomide at the investigator's discretion.

Hypertensive emergency ^a	
 Discontinue cabozantinib treatment
^a Hypertensive emergency is defined as uncontrolled elevated BP with clinical evidence of progressive or impending end-organ damage (e.g. myocardial infarction/ischemia, intracranial hemorrhage, cerebral ischemia, pulmonary edema, encephalopathy, kidney damage).	
Hand-foot Syndrome (PPES)	
Grade 1	
 Cabozantinib treatment may be continued at the current dose if PPES is clinically insignificant and tolerable. Otherwise, cabozantinib should be reduced to the next lower dose level. ^a Start urea 20% cream twice daily AND clobetasol 0.05% cream once daily. 
Reassess at least weekly; if PPES worsens at any time or does not improve after 2 weeks, proceed to the intervention guidelines for Grade 2.
 
 Continue temozolomide at the current dose.

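### Table 0-8 and Appendix A give different temozolomide rules for Grade 2 non-hematological toxicity, Table 0-8 lists Grade 3 under both stopping and reducing, and neither source is given precedence

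*Combined protocol and SAP*

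**What the plan says.** **Section 4.4.4, Table 0-8.** The non-hematological row is labelled "NCI-CTCAE non-hematological toxicity (except for alopecia, nausea and vomiting", with the bracket closed after vomiting. Its entries are Grade 2 for interruption, Grade 3 or 4 for discontinuation, and Grade 3 for reduction by one dose level.

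**Section 4.4.4, list under Table 0-8.** "Treatment with temozolomide may be continued when all of the following conditions are met": an ANC condition, a platelet condition, and non-hematological toxicity no worse than Grade 1, with the same three exceptions. Neither the row nor the list has a tolerability qualifier.

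**Appendix A.** The rows that give a temozolomide instruction by grade are:

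- Other treatment-related events, Grade 1 or tolerable Grade 2: "Continue cabozantinib and temozolomide treatment at the current dose; monitor as clinically indicated".
- Other events, intolerable Grade 2 or Grade 3: hold both drugs until Grade 1 or a tolerable Grade 2, then restart at the same dose or one level lower. Grade 3 events related to temozolomide require a one-level reduction, and Grade 4 events related to temozolomide stop it.
- Diarrhea, Grade 1-2 for under 48 hours: "If it does not improve with supportive measures consider a dose reduction. Continue temozolomide at the current dose". The dose reduction mentioned there is for cabozantinib.
- Diarrhea, intolerable Grade 2 or Grade 3: hold both drugs until Grade 1 or lower. "Dose reduce temozolomide by one dose level for Grade 3 only. Discontinue temozolomide for grade 4".
- Hand-foot syndrome (PPES), Grade 2: "Continue temozolomide at the investigator's discretion". Grade 3: "Interrupt/continue temozolomide at the investigator's discretion".
- Liver tests, Grade 2 for more than a week: hold both drugs until Grade 1.

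Sections 4.4 and 4.4.4 refer the reader to Appendix A for combination-related events. Neither says what to do where it differs from Table 0-8.

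**The concern.** Both sources are operative instructions for dosing a cytotoxic drug, and the trial runs at several centers. For some patients they give opposite answers on the same day. One site could give the full dose while another gives none, and each would depart from one part of the protocol while following another. At Grade 3, Table 0-8 alone supports two incompatible actions: permanent discontinuation, or continuing one level lower. What is at stake is patient safety and uniform treatment across sites.

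**Working it through.** No arithmetic applies. The check sets the two sources side by side for one patient on a temozolomide dosing day.

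| Situation | Table 0-8 and its list | Appendix A | Result |
|---|---|---|---|
| Tolerable Grade 2 fatigue, anorexia or weight loss | Hold until Grade 1 or lower | Give the current dose | Contradiction |
| Other event held as intolerable Grade 2, now tolerable Grade 2 | Still held | Restart, same dose or one level lower | Contradiction |
| Grade 2 diarrhea, under 48 h | Hold | Give the current dose | Contradiction |
| Intolerable Grade 2 diarrhea | Hold until Grade 1 or lower | Same | Agree |
| Tolerable Grade 2 diarrhea, over 48 h | Hold | No temozolomide instruction of its own; refers to Table 0-3, which interrupts study treatment | No contradiction |
| Grade 2 PPES | Hold | Investigator's discretion | Looser, but holding satisfies both |
| Grade 2 liver tests, over a week | Hold until Grade 1 or lower | Hold until Grade 1 | Agree |
| Grade 2 liver tests, shorter | Hold | No temozolomide instruction | Gap, not contradiction |
| Grade 3 diarrhea, or Grade 3 Other event related to temozolomide | Discontinue and also reduce | Reduce; discontinue at Grade 4 | Table 0-8 contradicts itself; its reduction column agrees with Appendix A |

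The hypertension and proteinuria rows are left out. They are written in mm Hg and urine protein/creatinine units, and the documents do not map those bands to CTCAE grades.

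**Is the double Grade 3 entry deliberate, or an extraction fault?** The other rows of Table 0-8 suggest neither.

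- ANC: discontinue below 0.5; reduce from 0.5 to below 1.0.
- Platelets: discontinue below 10; reduce from 10 to below 50.
- Non-hematological: discontinue at Grade 3 or 4; reduce at Grade 3.

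Stopping and reducing are kept apart in the first two rows and overlap only in the third.

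**Were the two sources meant to agree?** It appears so. Appendix A uses the same ANC cut-points as Table 0-8 (interrupt below 1.5, reduce below 1.0, discontinue below 0.5) and the same platelet limit for discontinuation (below 10). Its footnote also exempts nausea, vomiting and alopecia from temozolomide interruption, as Table 0-8 does. The non-hematological mismatch therefore looks like an error rather than a planned two-tier scheme.

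**Does anything rank them?** No. The references in 4.4 and 4.4.4 only direct the reader to Appendix A, and Table 0-8 follows the second of them with different rules. Appendix A's closing note limits adjustments by relation to cabozantinib and says nothing about precedence.

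**The case against.** The strongest reply is that the sources have different scopes: Table 0-8 for temozolomide toxicity, and Appendix A for toxicity of the combination, to which sites are sent twice. That gives sites a practical reading, but the separation does not hold. Appendix A contains its own rules for events related to temozolomide. Fatigue and diarrhea are listed as common with both drugs, in Sections 4.4.3 and 4.4.4, so attribution will often fail to pick the rule.

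Other parts of the reply stand. The conflict is not general across Appendix A: the PPES rows are discretionary, and the liver row agrees with Table 0-8 for the case it covers. At Grade 3 the main defect is a grade entered twice within Table 0-8.

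Several stronger readings are tempting and are not supported:

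- *Every Grade 2 rule in Appendix A contradicts Table 0-8.* The side-by-side comparison shows otherwise.
- *Table 0-8 stops any patient with a Grade 3 event for good.* That reads one column and ignores the one beside it.
- *Section 4.8 shows that Appendix A is the intended rule*, because it speaks of a tolerable Grade 2 or lower. It is a rule for removal from study treatment. It sets no threshold for giving temozolomide again and fits either source.
- *Held doses are lost under note j of the Study Procedures Table.* That note deals with visit windows, holidays and missed doses. It does not mention toxicity holds.

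**Conclusion.** Wrong as written, in two respects. First, the Grade 2 rules contradict each other for tolerable Other events, for the restart threshold after intolerable Other events, and for diarrhea of under 48 hours. Second, Table 0-8 assigns both stopping and reducing to Grade 3.

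The reach is limited. Temozolomide is given only on Days 1-5 (Section 4.3.1), so the Grade 2 conflict matters only when the toxicity is present on those days. An event that resolves between courses is dosed alike under both sources. The Grade 3 defect affects the decision to stop or reduce. The documents give no frequency for either situation, so the size cannot be stated as a number of patients or doses.

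A reader might infer that the conflict weakens the primary comparison of 20% with 39%. The documents do not support that: sample size and error rates do not depend on these rules. The conclusion assumes that the extracted table preserves the column positions, which the coherent ANC and platelet rows support.

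**What to change.** 1. State in Section 4.4.4 which source governs temozolomide for non-hematological events, and make the other match.
2. Set one Grade 2 hold and restart threshold in both places: either Grade 1 or lower throughout, or a tolerable Grade 2 allowed for Other events. This is a clinical safety choice for the sponsor, and the documents do not settle it.
3. Remove Grade 3 from one of its two Table 0-8 columns. Limiting discontinuation to Grade 4 would match Appendix A.
4. Keep an explicit temozolomide hold for Grade 2 diarrhea lasting over 48 hours, consistent with Table 0-3. A hold worded only for intolerable Grade 2 would lose it.
5. Say that Table 0-8 applies wherever Appendix A gives no temozolomide instruction, including Grade 2 liver tests of under one week and Grade 3-4 liver tests.

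The cost is wording in a protocol amendment and a memo to sites, with no added patients or procedures.
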